4.4. End-of-Study Definition

A participant is considered to have completed study treatment if she has taken all doses of the randomly assigned study treatment and completed the TOC Visit. A participant is considered to have completed the study if she has completed all study visits including the Follow-up Visit.

The end of the study is defined as the date of the last visit of the last participant in the study.

5. STUDY POPULATION

Prospective approval of protocol deviations to recruitment and enrollment criteria, also known as protocol waivers or exemptions, is not permitted.

5.1. Inclusion Criteria

Otherwise healthy participants are eligible to be included in the study only if all of the following criteria apply:

Age

1. The participant is ≥ 12 years of age at the time of signing the informed consent/assent and has a body weight ≥ 40 kg.

Note: Although participants as young as 12 years may enroll in the study, study sites must follow their institutional ethics committee and local country/national regulatory guidelines and enrollment will be contingent upon such approvals regarding the allowed lower age limit for clinical study participants.

Type of Participant and Disease Characteristics

2. The participant has 2 or more of the following clinical signs and symptoms of acute cystitis with onset < 96 hours prior to study entry: dysuria, frequency, urgency, or lower abdominal pain (see [Appendix 6](#)).
3. The participant has nitrite or pyuria (> 15 WBC/HPF or the presence of 3+/large leukocyte esterase) from a pretreatment clean-catch midstream urine sample based on local laboratory procedures.

Sex

4. The participant is female.

Contraceptive use should be consistent with local regulations regarding the methods of contraception for those participating in clinical studies.

- A female participant is eligible to participate if she is a woman of childbearing potential (WOCBP) who is not pregnant as confirmed by a high sensitivity urine pregnancy test at Baseline (Day 1) **regardless of current or prior contraception use or abstinence**, is not breastfeeding, or is not a WOCBP.

Note: Pregnancy testing requirements, contraceptive guidance, and WOCBP definitions are provided in [Appendix 2](#) and requirements for pregnancy testing during and after study treatment are located in [Appendix 8](#).

- Additional requirements for pregnancy testing during and after study treatment are located in [Appendix 8](#).
- The investigator is responsible for review of medical history, menstrual history, and recent sexual activity to decrease the risk for inclusion of a woman with an early undetected pregnancy.

Informed Consent

5. The participant is capable of giving signed informed consent/assent as described in [Appendix 3](#) which includes compliance with the requirements and restrictions listed in the informed consent form (ICF)/assent form and in this protocol.

5.2. Exclusion Criteria

Participants are excluded from the study if any of the following criteria apply:

Medical Conditions

1. The participant resides in a nursing home or dependent care type-facility.
2. The participant has a body mass index ≥ 40.0 kg/m² or a body mass index ≥ 35.0 kg/m² and is experiencing obesity-related health conditions such as uncontrolled high blood pressure or uncontrolled diabetes.
3. The participant has a history of sensitivity to the study treatments, or components thereof, or a history of a drug or other allergy that, in the opinion of the investigator or medical monitor, contraindicates her participation.
4. The participant is immunocompromised or has altered immune defenses that may predispose the participant to a higher risk of treatment failure and/or complications (e.g., uncontrolled diabetes, renal transplant recipients, participants with clinically significant persistent granulocytopenia [absolute neutrophil count $< 1000/\mu\text{L}$], and participants receiving immunosuppressive therapy, including corticosteroid therapy [> 40 mg/day prednisolone or equivalent for > 1 week, ≥ 20 mg/day prednisolone or equivalent for > 2 weeks, or prednisolone or equivalent ≥ 10 mg/day for > 6 weeks]). Participants with a known CD4 count of < 200 cells/mm³ should not be enrolled.
5. The participant has any of the following:
 - Medical condition that requires medication that may be impacted by inhibition of acetylcholinesterase, such as:
 - Poorly controlled asthma or chronic obstructive pulmonary disease at Baseline and, in the opinion of the investigator, not stable on current therapy
 - Acute severe pain, uncontrolled with conventional medical management
 - Active peptic ulcer disease

- Parkinson disease
- Myasthenia gravis
- A history of seizure disorder requiring medications for control (this does not include a history of childhood febrile seizures)

OR

- Known acute porphyria
 - Any surgical or medical condition (active or chronic) that may interfere with drug absorption, distribution, metabolism, or excretion of the study treatment (e.g., ileostomy or malabsorption syndrome)
6. The participant has a known glucose-6-phosphate dehydrogenase deficiency.
 7. The participant, in the judgment of the investigator, would not be able or willing to comply with the protocol or complete study follow-up.
 8. The participant has a serious underlying disease that could be imminently life-threatening, or the participant is unlikely to survive for the duration of the study period.

Urinary Tract Infection/Renal/Urogenital Exclusions

9. The participant has acute cystitis that is known or suspected to be due to fungal, parasitic, or viral pathogens; or known or suspected to be due to *Pseudomonas aeruginosa* or Enterobacterales (other than *E. coli*) as the contributing pathogen.
10. The participant has symptoms known or suspected to be caused by another disease process, such as asymptomatic bacteriuria, overactive bladder, chronic incontinence, or chronic interstitial cystitis, that may interfere with the clinical efficacy assessments or preclude complete resolution of acute cystitis symptoms.
11. The participant has an anatomical or physiological anomaly that predisposes the participant to UTIs or may be a source of persistent bacterial colonization, including calculi, obstruction or stricture of the urinary tract, primary renal disease (e.g., polycystic renal disease), or neurogenic bladder, or the participant has a history of anatomical or functional abnormalities of the urinary tract (e.g., chronic vesico-ureteral reflux, detrusor insufficiency).
12. The participant has an indwelling catheter, nephrostomy, ureter stent, or other foreign material in the urinary tract.
13. The participant who, in the opinion of the investigator, has an otherwise complicated UTI, an active upper UTI (e.g., pyelonephritis, urosepsis), signs and symptom onset ≥ 96 hours before study entry, or a temperature $\geq 101.4^{\circ}\text{F}$ ($\geq 38^{\circ}\text{C}$), flank pain, chills, or any other manifestations suggestive of upper UTI.
14. The participant has known anuria, oliguria, or significant impairment of renal function (creatinine clearance < 60 mL/min or clinically significant elevated serum creatinine as determined by the investigator).
15. The participant presents with vaginal discharge at Baseline (e.g., suspected sexually transmitted disease).

Cardiac Exclusions

16. The participant has congenital long QT syndrome or known prolongation of the corrected QT (QTc) interval.
17. The participant has uncompensated heart failure.
18. The participant has severe left ventricular hypertrophy.
19. The participant has a family history of QT prolongation or sudden death.
20. The participant has a recent history of vasovagal syncope or episodes of symptomatic bradycardia or brady arrhythmia within the last 12 months.
21. The participant is taking QT-prolonging drugs or drugs known to increase the risk of torsades de pointes (TdP) per the www.crediblemeds.org. “Known Risk of TdP” category at the time of her Baseline Visit, which cannot be safely discontinued from the Baseline Visit to the TOC Visit; or the participant is taking a strong cytochrome P450 enzyme 3A4 (CYP3A4) inhibitor.

Cardiac ECG Exclusions

22. For any participant ≥ 12 to < 18 years of age, the participant has an abnormal ECG reading at Baseline or during the study treatment.
23. The participant has a QTc > 450 msec or a QTc > 480 msec for participants with bundle-branch block.

Note:

- The QTc is the QT interval corrected for heart rate according to either Bazett’s formula (QTcB), or Fridericia’s (QTcF) formula, and/or another method. It is either machine read or manually overread.
 - The specific formula used to determine eligibility and discontinuation for an individual participant should be determined prior to initiation of the study. In other words, several different formulas cannot be used to calculate the QTc for an individual participant and then the lowest QTc value used to include or discontinue the participant from the trial.
24. The participant has a documented or recent history of uncorrected hypokalemia within the past 3 months.

Hepatic Exclusions

25. The participant has a known alanine aminotransferase (ALT) value $> 2 \times$ upper limit of normal (ULN).
26. The participant has a known bilirubin value $> 1.5 \times$ ULN (isolated bilirubin $> 1.5 \times$ ULN is acceptable if bilirubin is fractionated and direct bilirubin $< 35\%$).
27. The participant has cirrhosis or current unstable liver or biliary disease per investigator assessment defined by the presence of ascites, encephalopathy, coagulopathy, hypoalbuminemia, esophageal or gastric varices, or persistent jaundice.

Note: Stable noncirrhotic chronic liver disease (including Gilbert's syndrome, asymptomatic gallstones, and chronic stable hepatitis B or C [e.g., presence of hepatitis B surface antigen or positive hepatitis C antibody test result]) is acceptable if the participant otherwise meets entry criteria.

28. The participant has a previous history of cholestatic jaundice/hepatic dysfunction associated with nitrofurantoin.

Prior Antibiotic/Antifungal Use Exclusion

29. The participant has received treatment with other systemic antimicrobials or systemic antifungals within 1 week before study entry.

Concomitant Medication Use Exclusion

30. The participant plans to use any of the prohibited medications or nondrug therapies from the Baseline Visit through the TOC Visit as detailed in Section 6.5.2.

Prior/Concurrent Clinical Study Experience

31. The participant has been previously enrolled in this study or has previously been treated with gepotidacin.
32. The participant has participated in a clinical trial and has received an investigational product within 30 days or 5 half-lives, whichever is longer.

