8.2.2. Vital Signs

- Vital signs will be measured at the time points indicated in the SoA (Section 1.3).
- Vital signs will be measured in a semi-supine position after 5 minutes rest and will include temperature, systolic and diastolic blood pressure, and pulse rate.

- Vital sign measurements should be obtained before any blood draws scheduled on the same assessment day.
- Clinically significant changes from baseline will be reported as AEs.

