9.3. Populations for Analyses

For purposes of analysis, the following populations are defined:

Population	Description
Intent-to-Treat (ITT) Population	All participants randomly assigned to study treatment. Participants will be analyzed according to their randomized study treatment.

Population	Description
Microbiological ITT (micro-ITT) Population	All participants randomly assigned to study treatment who receive at least 1 dose of study treatment and have a qualifying baseline uropathogen (defined in Appendix 4), from a quantitative bacteriological culture of a pretreatment clean-catch midstream urine specimen. Participants will be analyzed according to their randomized study treatment.
Micro-ITT NTF-S Population	All participants in the micro-ITT Population whose baseline qualifying bacterial uropathogens all are susceptible to nitrofurantoin (NTF-S). Participants with missing MIC susceptibility results for any qualifying uropathogens will not be included in the NTF-S subpopulation. Participants will be analyzed according to their randomized study treatment. This is the primary analysis population.
Micro-ITT NTF-NS Population	All participants in the micro-ITT Population who have any qualifying baseline bacterial uropathogens that are not susceptible to nitrofurantoin (NTF-NS), defined as resistant to nitrofurantoin, intermediate to nitrofurantoin, or have no interpretation to nitrofurantoin. Participants with missing MIC susceptibility results for all qualifying uropathogens will not be included in the NTF-NS subpopulation. Participants will be analyzed according to their randomized study treatment.
Microbiologically Evaluable (ME) Population	Participants who meet the definition of the micro-ITT Population, follow important components of the study (as specified in the RAP) and have an interpretable quantitative urine culture at the specified visit. Note: Visit-specific ME populations will be defined in the RAP.
ME NTF-S Population	All participants in the ME visit-specific population whose baseline qualifying bacterial uropathogens all are susceptible to nitrofurantoin (NTF-S). Note: Visit-specific ME NTF-S populations will be defined in the RAP.
ME NTF-NS Population	All participants in the ME visit-specific population who have any baseline qualifying bacterial uropathogens that are not susceptible to nitrofurantoin (NTF-NS). Note: Visit-specific ME NTF-NS populations will be defined in the RAP.

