Allergic reaction	Pruritus without rash	Localized urticarial	Generalized urticarial; angioedema	Anaphylaxis
Headache	Mild, no treatment required	Transient, moderate; treatment required	Severe; responds to initial narcotic therapy	Intractable; requires repeated narcotic therapy
Fever: oral	37.7 to 38.5°C or 100.0 to 101.5°F	38.6 to 39.5°C or 101.6 to 102.9°F	39.6 to 40.5°C or 103 to 105°F	>40°C or >105°F
Fatigue	Normal activity reduced <48 hours	Normal activity decreased 25 to 50%; >48 hours	Normal activity decreased >50%; cannot work	Unable to care for self

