4.1. Protocol Deviations

Significant protocol deviations (including deviations related to study inclusion/exclusion criteria, conduct of the trial, participant management or participant assessment) will be summarized and listed. Separately, significant deviations which result in exclusion from analysis populations and events that result in exclusion from analysis populations will be summarized and listed.

Protocol deviations will be tracked by the study team throughout the conduct of the study in accordance with the Protocol Deviation Management Plan, entitled Study Deviation Tool and Rules.

- Data will be reviewed prior to freezing the database to ensure all significant deviations and deviations which may lead to exclusion of a participant from the analysis populations are captured and categorized in the protocol deviations dataset. This will occur prior to unblinding.
- This dataset will be the basis for the summaries and Listings of significant protocol deviations.

A separate Listing of all inclusion/exclusion criteria deviations will also be provided. This Listing will be based on data as recorded on the inclusion/exclusion page of the eCRF.

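### Exclusion criterion 13 gives one fever limit as 101.4 °F and 38 °C, but these are different temperatures, and neither document says which applies

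*Protocol*

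**What the plan says.** Protocol Section 5.2 opens with the rule "Participants are excluded from the study if any of the following criteria apply". Criterion 13 covers complicated and upper urinary tract infection. It leaves part of the decision to the investigator's judgement and then lists specific signs, including "a temperature $\geq 101.4^{\circ}\text{F}$ ($\geq 38^{\circ}\text{C}$), flank pain, chills, or any other manifestations suggestive of upper UTI". The Celsius value stands in parentheses after the Fahrenheit value, so it reads as the same limit in another unit.

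This is the only place in either document that states the eligibility temperature. Temperature appears otherwise in two settings:

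- **Vital signs.** Section 8.2.2 says the measurements "will include temperature, systolic and diastolic blood pressure, and pulse rate". Neither it nor the Schedule of Activities (Section 1.3, footnote j) gives a unit or a conversion rule.
- **Adverse event grading.** In the toxicity tables of Appendix 13, Grade 1 oral fever is "37.7 to 38.5°C or 100.0 to 101.5°F". That table grades events and does not set eligibility.

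Section 5 adds: "Prospective approval of protocol deviations to recruitment and enrollment criteria, also known as protocol waivers or exemptions, is not permitted".

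**The concern.** A numeric fever limit is there so that every site screens out possible upper urinary tract infection in the same way. If the two printed numbers are different temperatures, there is a range of readings in which a woman is excluded by one and admitted by the other. The SAP's regional subgroups (Section 5.4.2) name the United States, Bulgaria, Poland, Australia, India and South Korea, so it is reasonable to assume that both scales are in use across sites, although the documents do not say so.

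Two things are at stake: consistent eligibility decisions for isolated low-grade fever, and whether an enrolled woman in the range counts as an eligibility deviation. The second matters for reporting, because SAP Section 4.1 says: "Significant protocol deviations (including deviations related to study inclusion/exclusion criteria, conduct of the trial, participant management or participant assessment) will be summarized and listed".

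**Working it through.** **Inputs.** From Protocol Section 5.2, criterion 13: 101.4 °F and 38 °C. From Appendix 13, oral fever Grade 1: 37.7 to 38.5 °C, or 100.0 to 101.5 °F.

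**Formulas.** F = C × 9/5 + 32 and C = (F − 32) × 5/9.

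**Step 1: can the printed pair be reproduced?**

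- 38 × 9/5 + 32 = 100.4 °F, where the protocol prints 101.4 °F.
- (101.4 − 32) × 5/9 = 38.56 °C, where the protocol prints 38 °C.

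It cannot. The gap is 101.4 − 100.4 = 1.0 °F, or 38.56 − 38.00 = 0.56 °C.

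**Step 2: does rounding explain it?** 38.56 °C is 38.6 °C to one decimal and 39 °C to the whole degree. Neither gives 38 °C.

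**Step 3: which readings are in conflict?**

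| Reading (°C) | Equivalent (°F) | Meets ≥38 °C | Meets ≥101.4 °F |
|---|---|---|---|
| 37.9 | 100.22 | no | no |
| 38.0 | 100.40 | yes | no |
| 38.1 | 100.58 | yes | no |
| 38.2 | 100.76 | yes | no |
| 38.3 | 100.94 | yes | no |
| 38.4 | 101.12 | yes | no |
| 38.5 | 101.30 | yes | no |
| 38.6 | 101.48 | yes | yes |

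To one decimal, that is six Celsius readings (38.0 to 38.5) or ten Fahrenheit readings (100.4 to 101.3).

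**Step 4: does the protocol's own fever table use a looser conversion that would support the pair?** Converting the ends of the Grade 1 row gives 37.7 × 9/5 + 32 = 99.86 °F against 100.0 printed, and 38.5 × 9/5 + 32 = 101.3 °F against 101.5 printed. The row is approximate, but to within 0.2 °F. It sets 38.5 °C, not 38 °C, beside a value close to 101.4 °F. The Grade 4 entry in the same row (above 40 °C or above 105 °F) is out by 1 °F, since 40 °C is 104 °F, so the table is not a reliable reference for conversion. It neither explains the pair in criterion 13 nor settles which figure was meant. It does show that the whole conflict band lies within Grade 1 fever.

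**Step 5: does any text say which value governs?** The rule at the head of Section 5.2, that any one criterion is enough to exclude, leans towards the stricter reading (≥38 °C). But that rule works across criteria. It does not say how to read two unequal expressions of one limit inside a single criterion.

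**The case against.** The arithmetic is not open to dispute. The objections concern certainty and weight.

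- **Source.** The point turns on one digit that appears once, in text converted from PDF by a program. A misread cannot be ruled out. The surrounding text is clean and nothing suggests a misread, so this lowers confidence but does not remove the point.
- **Documents not seen.** The Protocol sends much site-level detail to the Study Reference Manual, and the eCRF is not available here. Either may already carry a single limit. The statement that no value governs holds only for the Protocol and SAP.
- **Investigator judgement.** A site worried by 38.2 °C can exclude the woman as possible upper infection whichever number is printed, and flank pain or chills would exclude her anyway. This stands, and it confines the problem to isolated low-grade fever. It does not make the numeric screen consistent between sites.
- **Waivers.** Section 5 forbids advance waivers, but enrolling a woman at 100.9 °F under the printed Fahrenheit limit is not a waiver. That is right. The ban means only that sites cannot settle the matter through approved exceptions.
- **Existing review.** Eligibility deviations are already to be summarized and listed. That review still needs one agreed limit before it can classify a reading in the band.

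**Conclusion.** The criterion is wrong as written: its two values differ by 1.0 °F (0.56 °C), and readings of 38.0 to 38.5 °C (100.4 to 101.3 °F) satisfy one and not the other. A slip for 100.4 °F is the likely cause, but the documents do not confirm it.

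The consequence is small. Under Protocol Section 9.3 the primary population depends on randomization, at least one dose, a qualifying baseline uropathogen and susceptibility to nitrofurantoin. Eligibility deviations do not remove anyone from it, so the primary analysis, type I error and power do not change. At most, classification could touch the microbiologically and clinically evaluable populations, which under SAP Section 4 drop women with a major deviation that prevents evaluation of efficacy. How many women fall in the band cannot be estimated, because no baseline temperatures are given.

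The conclusion rests on the signed protocol carrying the same digits as the text reviewed. Confidence is medium for that reason. Severity is minor.

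**What to change.** 1. Check criterion 13 in the signed PDF.
2. If the values are as read here, state one limit with a correct conversion. The default is ≥100.4 °F (≥38.0 °C), the stricter of the two. If the clinical team confirms that the Fahrenheit value was intended, write ≥101.4 °F (≥38.6 °C).
3. Confirm that the Study Reference Manual and any eCRF eligibility check use the same limit, and align them if they do not.
4. Within the deviation review already planned in SAP Section 4.1, query baseline temperatures of 38.0 to 38.5 °C (100.4 to 101.3 °F). Class them as eligibility deviations only if 38.0 °C is the confirmed limit.

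The cost is one document check, one clarification letter or a line in the next amendment, one eCRF check, and one query on a measurement already collected. Sample size and analysis do not change.

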5.3. Lifestyle Considerations

Participants will be requested to abstain from sexual activity from the Baseline Visit through the TOC Visit to prevent possible re-infection.

5.3.1. Meals and Dietary Restrictions

Study treatment should be taken after food consumption (a meal or a snack) and with water (see Section 6.1).

5.4. Screen Failures

Screen failures are defined as participants who consent to participate in the clinical study but are not subsequently randomized. A minimal set of screen failure information is required to ensure transparent reporting of screen failure participants to meet the Consolidated Standards of Reporting Trials (CONSORT) publishing requirements and to respond to queries from regulatory authorities. Minimal information includes demography, screen failure details, eligibility criteria, any protocol deviations and any SAEs.

Participants who are screen failures are allowed to be rescreened for the same infection episode or a subsequent infection episode and participate in the study if they meet all of the inclusion and exclusion criteria.

